#### The transient inhibitor incidence

- Numerators = Number of PUPs subjects who develop inhibitors and have subsequent negative results within 6 months, i.e. 183 days
- Denominators = Total number of PUPs who develop inhibitors

A two-sided 95% exact CI for the incidence of inhibitor formation will be calculated. If zero inhibitors are observed, then a one-sided 97.5% upper confidence limit will be calculated. SAS' FREQ procedure will be applied to produce an exact CI, which uses the Clopper-Pearson CI as the default method, however, Wald CIs will also be presented. The analysis will be performed also by race.

For PUPs, the incidence (with CI) of inhibitor formation to FVIII will be estimated also by Total EDs ranges. According to the Total EDs they were exposed at time of first positive FVIII inhibitor test PUPs will be classified into 0-10 EDs, >10-25 EDs, >25-50 and >50 EDs. Assessments at EDs=0 are defined as those assessments done before date and time or on the same date and time of first dose. If time of assessment or time of first dose is missing then the inhibitor result taken at the same date of the first dose will be considered as at EDs=0. An assessment done on the same date and time of a dose will be considered to be exposed to the number of EDs the subject has been exposed before that date and time. If time is missing for the assessment or the dose, then the assessment done on the same date of dose will be considered to be exposed to the EDs the subject has been exposed before the date of that dose.

Summaries of inhibitors assay test and inhibitor titer while subjects are inhibitor positive will be provided.

The incidence of inhibitor formation to FVIII will be also summarized at the assessment of 10, 50 and 100 EDs in the current study as collected in the eCRF.

Analysis will be performed overall, by region and considering the Japanese subgroup only.

CCI

CCI

CCI

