Inhibitors are typically classified as either high- or low-responding, depending on how an individual's immune system is stimulated following repeated exposures to FVIII. High-responding inhibitors can rise quickly to very high levels (Bethesda titer ≥ 5 units) if the immune system reacts briskly or strongly to repeated exposure to FVIII. In high-titer inhibitors without continued exposure (a period of months or years), the titer level could decrease to a low level. Low-responding inhibitors demonstrate a slower or weaker responding immune system and the Bethesda titer will remain low (Bethesda titer < 5 units). However, the characteristics of an inhibitor can change over time. Low-titer inhibitors may also disappear spontaneously within several weeks or months, achieving immune tolerance in patients [[DiMichele, 2008](#)].

“The union of Factor VIII with its inhibitor is not associated with allergic reactions. The presence of an inhibitor does not change the typical site, frequency, or severity of bleeding, however the inhibitor makes control of hemorrhages more difficult.” [Kasper, 2004].

Inhibitor development usually occurs between a median age of 1.7 and 3.3 years regardless of the replacement factor product used, and occurs less frequently after the age of 5 years. Inhibitors are generally detected between a mean of 9 and 21 exposure days (EDs) with a median of 12 EDs following exposure to factor replacement products. Inhibitor development is most commonly detected within the first 50 EDs, and new inhibitors are rarely detected after 200 treatment days with the replacement factor [DiMichele, 2002].

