### 2.2.2 Secondary Safety Endpoints

The secondary Safety endpoints of the study are:

In **Arm 1 and Arm 3 (PTPs)**, the secondary safety endpoints are:

- Incidence of inhibitor formation to FVIII in at least 200 PTPs after 10 EDs and after 50 EDs with rVIII-SingleChain.
- Percentage of PTPs who develop antibodies against rVIII-SingleChain.
- Percentage of PTPs who develop antibodies to CHO proteins.

In **Arm 2 (PUPs)**, the secondary safety endpoints are:

- Incidence of high-titer inhibitor formation to FVIII after 10 EDs with rVIII-SingleChain in at least 50 PUPs.
  - A positive inhibitor is defined as two consecutive positive results ( $\geq 0.6$  Bethesda units (BU) /mL from the central lab.
  - The high-titer inhibitor is defined as any inhibitor tier of  $\geq 5$  BU/mL) during the study.
- Incidence of low-titer inhibitor formation (FVIII after 10 EDs and after 50 EDs with rVIII-SingleChain in at least 50 PUPs.

- The low-titer inhibitor is defined as any inhibitor tier of  $\geq 0.6$  and  $< 5$  BU/mL) during the study.
- Incidence of total (low- and high-titer) inhibitor formation to FVIII after 10 EDs and after 50 EDs with rVIII-SingleChain in at least 50 PUPs.
- Incidence of transient inhibitors (negative results within 6 months after diagnosis)
- Percentage of PUPs who develop antibodies against rVIII-SingleChain.
- Percentage of PUPs who develop antibodies to CHO proteins.
- Percentage of PUPs with clinically significant abnormal values for blood pressure, or heart rate, or body temperature at 1, 2, 3, or 6 hours after the first rVIII-SingleChain injection.
- Percentage of PUPs with treatment-emergent clinically significant abnormal values for blood pressure, heart rate, or body temperature during the course of the study.

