### 3.5.6 Subgroups/Subpopulations

The following subgroups will be defined:

- Age based on age in this study:
  - For PTPs (Arm 1 and Arm 3): 0 to < 6 years,  $\geq 6$  to < 12 years,  $\geq 12$  to < 18 years and  $\geq 18$  to  $\leq 65$  years, 0 to <12 years,  $\geq 12$  to  $\leq 65$  years;
- By Region (Europe, US, Rest of the world, Asia)
- Japan subgroup

Efficacy endpoint will be analyzed by

- Positive vs. negative test for non-inhibitory Anti-Drug Antibodies (ADAs) during the Study.

The incidence of inhibitors will be summarized by

- Race (White, Black, Asian, and Other)

Annualized Bleeding Rates will be presented by

- ADA status (Positive and Negative)

For PUPs analyses for Annualized Bleeding Rates, hemostatic efficacy, TEAE and IR will be presented by inhibitor status (Positive and Negative) at the time of assessment.

CCI

Analyses by inhibitor status or inhibitor group have been defined in this SAP within relevant sections, the definition of inhibitor status and inhibitor group are the following ones:

*Inhibitor positive*

A subject is inhibitor positive if he developed a titre value (from the central lab) of at least 0.6 BU/mL, and was also confirmed in the next assessment with a titre value of at least 0.6 BU/mL.

*Inhibitor negative*

[figure not shown]
A subject is inhibitor negative if his titre value (from the central lab) was below 0.6 BU/mL.

*Inhibitor eradicated*

It refers to a subject who was previously documented with a confirmed inhibitor positive titre result and at a later point in the study, his titre value decreased and became low enough to classify him as inhibitor negative (titre value < 0.6 BU/mL). However, in order to become inhibitor eradicated, an inhibitor positive subject must first present an initial inhibitor negative titre result which must be confirmed in the next assessment by another inhibitor negative titre result.

*Inhibitor status*

A subject's inhibitor status represents a period in the study in which he is either inhibitor positive (+) or inhibitor negative (-), depending on his titre value at a given time.

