The above schema depicts a subject starting out as a negative inhibitor (-), which is the case for all subjects in the study. At some point in the study, i.e. at Time (c), his titre level went up and met the criteria for inhibitor positive status (+), which consisted of an initial titre value of  $\geq 0.6$  BU/mL, represented by (+) at Time (c), and was followed by a confirmatory titre value of  $\geq 0.6$  BU/mL in the next assessment, represented by (+)\* at Time (d). At Time (c), he is considered (+). When a subject becomes (+), the Investigator may administer an intensified prophylaxis (IP) treatment. Furthermore, he will be included in the CCI [REDACTED] to treat his inhibitory response to rVIII-SingleChain treatment. If the subject responds positively to IP and/or CCI [REDACTED], his titre values will improve (i.e. decrease) at later assessments. In the above schema, the subject became (-) at Time (e), which was followed by a confirmatory assessment (-)\* at Time (f) one month later. At Time (f), the subject is considered inhibitor eradicated.

From the above schema, we can state that:

Period of (+): Time reference after Time (c) up to Time (f), or Time (c) < Time reference  $\leq$  Time (f).

Period of (-): There will be two: on or before (+), and after (-)\*.

- On or before (+): Time (start) < Time reference  $\leq$  Time (c)
- After (-)\*: Time (f) < Time reference  $\leq$  Time (End)

By partitioning the study duration as periods of inhibitor status, analysis of time-dependent variables can be presented by inhibitor status.

*Inhibitor group*

An inhibitor group classifies a subject's inhibitor status overall during the study. Therefore, this classification is fixed for a subject, which differentiates itself from the classification by

inhibitor status for which a subject's inhibitor status may change from (-) to (+) over time according to his titre values.

The inhibitor positive group comprises of subjects who were confirmed (+) at any point during the study.

The inhibitor negative group comprises of subjects who were always (-) during the study.

For all subgroups defined in this section, in case of patients lower or equal than 3, the table will not be produced, data will only be provided in the listings.

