##### The Inhibitor incidence after 100 Total EDs

- Numerators = Number of PTP subjects who develop inhibitors up to 100 EDs ( $\leq 100$  EDs)
- Denominators = Total number of PTPs with at least 100 EDs ( $\geq 100$  EDs) + subjects with less than 100 EDs with inhibitors. Subjects not tested at  $\leq 100$  EDs will be excluded.

CCI

Same algorithm will be applied for PUPs.

For PUPs incidence of transient inhibitors (negative results within 6 months after positive result) will be also provided.

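### The transient-inhibitor rule does not say how many negative results it needs, does not separate treated boys, and counts boys not observed to day 183 as not transient

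*SAP*

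**What the plan says.** The numerator in SAP 4.7.1 (The transient inhibitor incidence) is "Numerators = Number of PUPs subjects who develop inhibitors and have subsequent negative results within 6 months, i.e. 183 days". The denominator is "Denominators = Total number of PUPs who develop inhibitors". The start of the six months is worded in two ways. SAP 2.2.2 has "Incidence of transient inhibitors (negative results within 6 months after diagnosis", and the text of 4.7.1 has "For PUPs incidence of transient inhibitors (negative results within 6 months after positive result) will be also provided".

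Other SAP rules bear on this:

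- **Single negative.** SAP 3.5.6 states: "A subject is inhibitor negative if his titre value (from the central lab) was below 0.6 BU/mL".
- **Eradication.** Under the same section the boy "must first present an initial inhibitor negative titre result which must be confirmed in the next assessment by another inhibitor negative titre result". Until that second negative he stays in the inhibitor-positive period.
- **Positive result.** It must be confirmed by a second positive (SAP 2.2.2, 3.5.6 and 4.7.1).
- **Untested subjects.** The incidences after 10, 50 and 100 exposure days exclude them (SAP 4.7.1). The transient rule has no such exclusion.

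On treatment, SAP 3.5.6 notes: "When a subject becomes (+), the Investigator may administer an intensified prophylaxis (IP) treatment". Protocol 3.3 allows an inhibitor treatment period of up to 24 months in the main study. Protocol 1.1 describes loss without treatment separately: "Low-titer inhibitors may also disappear spontaneously within several weeks or months".

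**The concern.** The rule leaves three choices open, and each changes who is counted.

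1. **Number of negatives.** A boy with a confirmed inhibitor, one negative and then another positive can meet the numerator, although SAP 3.5.6 still classes him as inhibitor positive.
2. **Treatment.** A boy who turns negative on intensified prophylaxis, after an inhibitor-directed dose adjustment or in the inhibitor-treatment substudy is counted together with a boy whose inhibitor went away untreated. These are different clinical findings reported as one percentage.
3. **Observation.** A boy who leaves or is not sampled before day 183 stays in the denominator and cannot enter the numerator. Protocol 4.2.1 makes some withdrawals mandatory, for example a confirmed high-titer inhibitor in a boy unwilling to join the substudy. SAP 4.12.2 applies no imputation here.

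The first two can raise the figure and the third lowers it. At stake is whether an added secondary safety endpoint with a very small denominator can be programmed in only one way and read without doubt.

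**Working it through.** **The plan's own figure.** The SAP month is 30.4375 days (4.5.1): 6 × 30.4375 = 182.6, rounded up to 183. The figure reproduces. The protocol's 28-day month would give 6 × 28 = 168 days.

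**Clock start.** If diagnosis means the confirming sample, the two starts differ by the gap between first and confirming positive: 28 or 84 days on scheduled visits, less if the repeat is expedited.

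**Effect of one boy.** Inputs are 24 boys (Protocol 11.1) and 35.4% inhibitor incidence (the randomized study cited in Protocol 1.1), used only to size the denominator: 0.354 × 24 = 8.5. I use 8. One boy is 1/8 = 12.5 points; with 6 or 12 inhibitor-positive boys it would be 16.7 or 8.3. Exact 95% intervals for n = 8:

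| Transient | Estimate | 95% CI |
|---|---|---|
| 0/8 | 0% | 0 to 36.9 |
| 1/8 | 12.5% | 0.3 to 52.7 |
| 2/8 | 25.0% | 3.2 to 65.1 |

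**Single negative against confirmed negative.** On prophylaxis, visits are 28 days apart until 25 exposure days and then three-monthly (Protocol 8.10.2), which is 84 days at 28 days per month. Samples in the window: 183/28 gives 6 and 183/84 gives 2. Protocol 8.6 asks for a repeat as soon as possible after a positive; if that is an extra sample, 6 and 2 stand. SAP 4.7.1 speaks of re-testing at a subsequent visit; if the confirming positive uses a scheduled visit, 5 and 1 remain.

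Let f be the chance that a persistent inhibitor gives a negative on one sample. The documents give no value, so f = 2%, 5% and 10% are assumptions, as is independence between samples. The chance of at least one negative in k samples is 1 − (1 − f)^k.

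| k | f = 2% | f = 5% | f = 10% |
|---|---|---|---|
| 6 (28-day visits) | 11.4% | 26.5% | 46.9% |
| 5 (28-day visits) | 9.6% | 22.6% | 41.0% |
| 2 (84-day visits) | 4.0% | 9.8% | 19.0% |
| 1 (84-day visits) | 2.0% | 5.0% | 10.0% |

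If two consecutive negatives are required inside the window, the chance is 0.2%, 1.2% or 4.6% with 6 samples and 0.04%, 0.25% or 1.0% with 2. If the second negative may fall after day 183, there are k possible first negatives, so the chance is at most k × f²: 0.24%, 1.5% or 6% for k = 6, and 0.08%, 0.5% or 2% for k = 2. The gain is kept almost in full.

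**Treatment.** No assay assumption is needed. Protocol 1.1 gives eradication in approximately 70% to 85% with immune tolerance induction, over a few months to 2 or more years. A treated boy turning negative within 183 days is therefore a realistic case, and each one counts 12.5 points when n = 8.

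**The case against.** Several stronger readings are tempting, and the documents do not support them.

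- **That the SAP adopts a single unconfirmed negative.** It does not. All three statements of the endpoint speak of negative results in the plural and give no number. The text permits a single negative by silence.
- **That a positive, a 0.4 BU/mL result and a positive make a boy transient.** Under SAP 3.5.6 and 4.7.1 the first positive is then unconfirmed, and on that sequence alone he has no inhibitor. The problem needs two consecutive positives first.
- **That counting treated boys contradicts the definition.** No visible text defines transient as untreated or spontaneous, so this is a gap in interpretation.
- **That the figure is biased upward.** Boys not observed to day 183 pull it down.
- **That substudy boys are not handled.** Redacted blocks lie close to the transient rule and may cover them. Intensified prophylaxis and main-study inhibitor treatment are not redacted, and the visible rule has no condition for either.

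The case for leaving the text alone is that this is a descriptive secondary endpoint with no p-values planned and very wide intervals. Confirmed inhibitors are serious adverse events (Protocol 9.1.3), and titers are plotted by subject (SAP 4.7.4.1), so a reader could check each case. That limits the harm, but it does not settle how the percentage is to be computed.

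**Conclusion.** The point holds as an ambiguity and a gap. As written, the rule can call a boy transient while the SAP's own status rule keeps him inhibitor positive, it pools loss under treatment with loss without treatment, and it counts boys not observed to day 183 as not transient.

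A reader might go further and infer that persistent inhibitors will be misreported. That depends on programming and data the documents do not show, and the direction of the net error is unknown. The 12.5 points per boy rest on an assumed 8 inhibitor-positive boys. The single-negative figures rest on assumed, independent error rates and on regular prophylaxis visits; on-demand visits follow doses, so their number varies. The primary high-titer endpoint is not affected. This is a cheap improvement worth making before the analysis.

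**What to change.** Reword the transient rule in SAP 4.7.1 and align 2.2.2 with it:

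1. Start the clock at the first positive sample of a confirmed inhibitor.
2. Count a boy as transient only if a central-laboratory result below 0.6 BU/mL within 183 days is confirmed by a negative at the next assessment, as in the SAP's eradication rule. Allow the confirming result to fall after day 183, because 84-day visits give only one or two usable samples in the window.
3. Report the result separately for boys with and without inhibitor-directed treatment before the negative.
4. Report relapse after a confirmed negative on its own line. An open-ended condition of no later positive would make the classification depend on length of follow-up, and Protocol 4.2.1 and 9.10 already treat recurrence as a separate event.
5. List boys without sampled follow-up to day 183 and without an earlier confirmed negative as not assessable, and give the rate with and without them. State what counts as sampled to day 183 when visits fall at days 84, 168 and 252.

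This changes analysis wording only. Central titers are collected (Protocol 8.6.1), regimen changes are recorded (Protocol 3.2.5) and the reason for dose adjustment is already summarized (SAP 4.5.4). The case report form is not visible, so it should be checked that inhibitor-directed changes can be identified. The cost is that the reported transient percentage may fall and that the treated and untreated groups will hold only a few boys each.

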4.2 Subject Withdrawal

4.2.1 Subject Withdrawal

Subjects may withdraw from the study at any time at their own request, or they may be withdrawn at any time at the discretion of the investigator or CSL for safety, behavioral or administrative reasons (eg, due to an AE, protocol violation, subject noncompliance, and study termination).

In accordance with ICH principles of GCP, the investigator always has the option to advise a subject to withdraw from the study if the subject's safety or well-being is compromised by his or her further participation in the study. Concern for the interests of the subject must always prevail over the interests of the study.

If a subject is withdrawn from the study or further participation is declined, they will continue to have access to medical care and will be treated as per routine medical practice.

Arm 2 (PUPs):

In addition to the general withdrawal criteria described above, PUPs in Arm 2 **must be withdrawn** from the study if they develop any of the following withdrawal criteria:

- Use of any FVIII product other than rVIII-SingleChain (or its marketed available version) during the study (including if used as rescue medication).
- Subject develops a confirmed high-titer inhibitor (> 5 BU/mL confirmed by repeat testing at the central laboratory) but is not willing to participate in the **CCI** substudy.
- If the subject in the main study or the **CCI** substudy has successful inhibitor eradication and experiences inhibitor recurrence (relapse; ie, 2 consecutive inhibitor results \geq 0.6 BU/mL after eradication).

Further withdrawal criteria specific to the **CC1** substudy are defined in [Appendix 1](#).

Subjects with a **low-titer** inhibitor may either continue in the main study or can be enrolled into the **CC1** substudy (see [Appendix 1](#)), at the discretion of the investigator after discussion with the sponsor.

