9.10 Follow-up of Inhibitor SAEs in Arm 2 (PUPs)

PUPs in Arm 2 who develop an inhibitor SAE (ie, low-titer or high-titer inhibitors confirmed by the central laboratory) will be followed up for **28 days after their End of Study Visit**. All follow-up information (and attempted follow-up contacts) should be documented in the subject's medical records and submitted to CSL Global Clinical Safety and Pharmacovigilance. At a minimum, the following specific information should be documented and submitted:

- Information on last inhibitor titer.
- Details and outcome of major / life-threatening bleeding episodes.

- Hemophilia treatment since End of Study Visit:
 - Treatment modality (on-demand, prophylaxis).
 - Currently receiving CCI [REDACTED]
 - CCI [REDACTED]
 - Treatment with bypassing agents (yes, no).
- AEs since End of Study Visit.
- Development of inhibitor after previous eradication. In the event of inhibitor development after previous eradication, this will be considered a new SAE and should be reported as such.

10 Assessments

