### 4.12.2 Early Withdrawal or Missing data

Refer to the handling of partial dates in [Section 4.12.1](#) and method of analysis for the primary efficacy endpoint in [Section 4.6.1.1](#). Other than these two items, no imputation due to withdrawals or missing data will be applied.

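### The transient-inhibitor rate in PUPs is only a lower bound: a boy who leaves before 183 days with no negative titer on record is scored as not transient

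*SAP*

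**What the plan says.** **The endpoint.** SAP section 2.2.2 lists, among the PUP secondary safety endpoints, "Incidence of transient inhibitors (negative results within 6 months after diagnosis". SAP section 4.7.1 gives the calculation. The numerator is "Number of PUPs subjects who develop inhibitors and have subsequent negative results within 6 months, i.e. 183 days". For the divisor it states "Denominators = Total number of PUPs who develop inhibitors". It sets no minimum follow-up, no retest condition and no censoring rule. The incidences after 10, 50 and 100 EDs in the same section do leave out subjects who were not tested.

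**Leaving early.** Protocol section 4.2.1 lets any subject withdraw at any time. It also requires withdrawal of a PUP in these situations, among others:
- "Subject develops a confirmed high-titer inhibitor (> 5 BU/mL confirmed by repeat testing at the central laboratory) but is not willing to participate" (the refusal concerns the substudy);
- "Use of any FVIII product other than rVIII-SingleChain (or its marketed available version) during the study (including if used as rescue medication").

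Under Protocol section 8.10.6, premature discontinuation triggers the End of Study Visit, after which only AE and inhibitor-SAE follow-up continues.

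**After leaving.** Protocol section 9.10 says "PUPs in Arm 2 who develop an inhibitor SAE (ie, low-titer or high-titer inhibitors confirmed by the central laboratory) will be followed up for"; the period stated there is 28 days, counted from the End of Study Visit. The minimum data set includes the last inhibitor titer. No central-laboratory retest is scheduled.

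**Missing data.** SAP section 4.12.2 says that, apart from partial dates and the primary efficacy endpoint, "no imputation due to withdrawals or missing data will be applied".

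**The concern.** To call an inhibitor not transient, one has to watch it for the whole 183 days without seeing it clear. The divisor in SAP section 4.7.1 does not require that. A boy shown to be positive for six months and a boy who left after a few weeks with no negative result get the same score.

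The error can only go one way. A negative result that nobody looked for cannot enter the numerator, while the boy stays in the denominator. Few inhibitor cases are expected, so one or two such boys would change the reported rate visibly. The reader of the table could not tell persistence from lack of observation.

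**Working it through.** **1. The plan's own figure.** SAP section 4.5.1 uses a month of 30.4375 days. 6 × 30.4375 = 182.6, which rounds to the stated 183 days. (The 28-day month in the protocol's visit schedules would give 168.) The documents state no expected transient rate, so nothing else can be reproduced.

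**2. Who cannot be observed for the whole window.** The 28 days of inhibitor follow-up run from the End of Study Visit, not from the positive test. 183 − 28 = 155. A boy whose End of Study Visit comes less than 155 days after his first positive is not covered to day 183. This gives full credit to the 28 days, although no central-laboratory test is scheduled in them.

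**3. Bias formula.** Let
- m = PUPs who develop an inhibitor;
- w = those who leave before the window closes with no negative on record;
- pS, pW = probability of turning negative by day 183 in the boys who stay and in those who leave.

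Expected rate under the SAP rule = (m − w) × pS / m.

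Rate with complete follow-up = [(m − w) × pS + w × pW] / m.

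Bias = −w × pW / m. It is never positive, and it is zero if w = 0 or pW = 0.

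**4. Inputs for an illustration.**
- At least 24 PUPs (Protocol section 11.1; SAP section 3.9, Sample Size Estimation).
- 35.4% inhibitor incidence, low and high titer together, from the published study cited in Protocol section 1.1. It is used only for scale: 24 × 0.354 = 8.5, so m = 8 is assumed.
- w and pW are not given in the documents and are varied.

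**5. Bias in percentage points, m = 8.**

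| Early leavers w | pW = 0 | pW = 10% | pW = 30% | pW = 50% |
|---|---|---|---|---|
| 1 | 0 | −1.25 | −3.75 | −6.25 |
| 2 | 0 | −2.5 | −7.5 | −12.5 |
| 3 | 0 | −3.75 | −11.25 | −18.75 |
| 4 | 0 | −5.0 | −15.0 | −25.0 |

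For example, with w = 2 and pS = pW = 50%, the true 50% is reported on average as 6 × 0.5 / 8 = 37.5%.

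**6. What a table could show.** Suppose 8 cases, 3 observed clearances and 2 boys who left early with no negative (exact Clopper-Pearson 95% intervals):
- SAP rule: 3/8 = 37.5% (8.5 to 75.5);
- the 6 evaluable boys only: 3/6 = 50.0% (11.8 to 88.2);
- leavers counted as transient: 5/8 = 62.5% (24.5 to 91.5).

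The same data support anything from 37.5% to 62.5%, depending only on how the two unobserved boys are scored.

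**The case against.** Several stronger readings are tempting, and the documents do not support them.

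- **That high-titer boys leave as a rule.** Only those who decline the substudy must be withdrawn. Low-titer boys may stay in the main study or join the substudy (Protocol section 7.1). For boys who stay in the main study, inhibitor treatment can run to 24 months, with 12 months more after eradication (Protocol section 3.3), well past 183 days.
- **That any use of another FVIII product distorts this rate.** It matters only if the boy is already inhibitor-positive. Bypassing agents, permitted in subjects with inhibitors, do not trigger withdrawal.
- **That an early leaver has no chance of being counted as transient.** A negative before withdrawal counts, and the End of Study Visit itself includes an inhibitor sample (Protocol section 8.10.6.2). A boy who leaves 155 days or more after his positive loses little or nothing.
- **That the rate is certainly too low.** Protocol section 1.1 links spontaneous disappearance to low-titer inhibitors. For high-titer ones without further exposure it describes a fall to a low level over months or years. On the high-titer route pW may be near zero, and then so is the bias.
- **That a Kaplan-Meier estimate would put it right.** Withdrawal triggered by a high titer is informative censoring. In the example above, if the two leavers would never have cleared, the truth is 37.5% and the SAP rule is right. Censoring them before any clearance gives 3/6 = 50%.
- **That SAP section 4.12.2 rules out any handling.** It limits imputation. It does not forbid bounds or a not-evaluable row.

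The other side is also right that the endpoint is modest: Protocol section 2.2.2.2 does not list it, and SAP section 4.11 says that it was added for completeness. Some of the missing information can be recovered from the by-subject titer plots and the disposition table. Text near this rule in SAP section 4.7.1 is blacked out, so a related provision there cannot be excluded.

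What remains is that the visible rule reports an unobserved outcome as persistence, and the rate itself does not say so.

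**Conclusion.** The point holds as a matter of labeling and completeness. The rate in SAP section 4.7.1 is a lower bound on what testing every case for 183 days would have shown. The direction follows from the definition. The size does not: it depends on how many inhibitor-positive boys leave early with no negative and how many of them would have cleared, and the documents give neither. With 8 assumed cases and 2 early leavers, the range is 0 to −12.5 points for a clearance probability of 0 to 50%. It is exactly zero if nobody leaves early or no leaver would have cleared.

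This is a minor point. The endpoint is descriptive, no decision depends on it, and the primary inhibitor incidence is not affected.

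**What to change.** In SAP section 4.7.1, under the transient inhibitor incidence:

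1. Keep the current rate and label it the lower bound.
2. Add the upper bound, which counts as transient each boy with fewer than 183 days of central-laboratory titers and no negative result.
3. Report the number of those boys in a separate row: not evaluable (<183 days of titers, no negative).
4. Show a Kaplan-Meier estimate of time to first negative only as supportive, if at all, noting that titer-triggered withdrawal is informative censoring and can bias it upward.

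Dropping the early leavers from the denominator is not a substitute. With w = 2, m = 8 and pW = 0 it overstates the rate by 7.5 points (pS = 30%) to 12.5 points (pS = 50%).

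The cost is one SAP paragraph, the upper-bound figure and one more table row, all from titers already collected. The downside is that the range between the bounds will be wide with so few cases, which is an honest picture of what the data can show.
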